### 11.2.3 Serious Adverse Events

Serious adverse events will be reportable from the time the time of first dose through the End of Study Visit (scheduled for approximately 28 days post last IMG-7289 dose) or until the Investigator and Imago BioSciences determine that follow-up is no longer necessary. Serious adverse events that are suspected to be drug related will be reported even if they occur when the patient is no longer on the study.

**Note:** In the UK, serious AEs (SAEs) will be recorded from time of consent through the EoS or until the Investigator and Imago BioSciences determine that follow-up is no longer necessary.

An SAE is any AE that results in any of the following outcomes:

#### **Death\***

**Life-threatening experience.** Any adverse event that places the patient, in the view of the reporter, at immediate risk of death from the adverse event as it occurred, i.e., does not include an adverse event that had it occurred in a more severe form, might have caused death.

**Required or prolonged inpatient hospitalisation\*.** The adverse event resulted in an initial inpatient hospitalisation or prolonged an existing hospitalisation of the patient. If a patient is hospitalised as part of the clinical use of the product, a period of normal hospitalisation will be

outlined in the protocol or by the judgment of the Investigator. Hospitalisations longer than this period will be prolonged hospitalisations.

**Persistent or significant disability/incapacity.** An adverse event that resulted in a substantial disruption of a person's ability to conduct normal life functions.

**Congenital Anomaly.** The exposure of the patient to the drug or biologic during pregnancy that is judged to have resulted in the congenital anomaly/birth defect.

**Important medical events.** Adverse events that may not result in death, be life-threatening, or require hospitalisation may be considered a serious adverse event when, based upon appropriate medical judgment, may jeopardise the patient or subject and may require medical or surgical intervention to prevent one of the outcomes listed above. Important medical events or interventions may be considered an SAE based upon medical judgment of the Investigator.

**\*Note:** Hospitalization consistent with progression of underlying malignancy should NOT be reported as an SAE. An SAE with an outcome of death solely due to progression of the underlying malignancy does not need to be reported as an SAE.

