Many chromosomal and genetic abnormalities have also been identified in the MPNs. Some, like deletions of chromosome 20q, may be antecedent cytogenetic abnormalities that predispose to mutations in *JAK2* or are epistatic, that together determine the subsequent clinical course. The underlying mechanisms that generate the common pathogenic mutations, and the antecedent and subsequent mutations necessary to cause clinical disease and to shape the natural history remain a mystery. In light of the unfruitful search for additional highly recurrent mutations with whole genome sequencing, these influences may be specific to the cell of origin in which the mutations arose, epigenetic and even physiologic, considering the reportedly worse natural history of polycythaemia in women compared to men (Spivak *et al.*, 2014).

Some MPN patients are asymptomatic at the time of diagnosis, and PV, ET and MF can be difficult to clinically distinguish. Common presenting manifestations can include stroke, fatigue, weight loss, night sweats, fever, dyspnea, and abdominal discomfort owing to splenomegaly. Leukocytosis, thrombocytosis and splenomegaly can be present. Major complications arise from cytopenias secondary to bone marrow failure, extramedullary haematopoiesis (principally in the spleen and liver), and evolution to AML. Splenomegaly is for many patients the most distressing complication of

myelofibrosis leading to discomfort, inanition, splenic infarction, portal and pulmonary hypertension, and blood cell sequestration, while thrombosis is the dreaded complication of elevated red blood cell mass.

Myelofibrosis associated with somatic mutations in haematopoietic stem/progenitor cells is a progressive neoplastic disorder with a median lifespan of 5.5 years from the time of diagnosis, a shorter mean survival time compared to PV and ET (Hultcrantz *et al.*, 2015). Death most often results from the consequences of thrombocytopenia or neutropenia, haemorrhage or infection (Malak *et al.*, 2012). Complications exacerbating morbidity secondary to anaemia and extramedullary haematopoiesis include portal hypertension and heart failure.

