Progression of underlying malignancy is not reported as an AE if it is consistent with the suspected progression of the underlying cancer. Clinical symptoms of progression may be reported as AEs if the symptom cannot be determined as exclusively due to the progression of the underlying malignancy or does not fit the expected pattern of progression for the disease under study. If there is any uncertainty about an AE being due to only the disease under study, it should be reported as an AE.

It is important Investigators record accurate AE terms in the eCRFs. Wherever possible, a specific disease or syndrome rather than individual associated signs, symptoms or laboratory parameter will be identified by the Investigator and recorded in the eCRF. However, if an observed or reported sign, symptom or laboratory parameter is not considered a component of a specific disease or syndrome by the Investigator, or is atypical, it should be recorded as a separate AE in the eCRF.

Disease signs, symptoms, and/or laboratory abnormalities already existing prior to the use of the investigational product are not considered AEs after treatment unless they reoccur after the patient has recovered from the preexisting condition or in the opinion of the Investigator they represent a clinically significant exacerbation in intensity or frequency.

Clinical significance is defined as any variation in signs, symptoms, or testing that has medical relevance and may result in an alteration in medical care. The Investigator will continue to monitor the patient until the assessment returns to Baseline or until the Investigator determines that follow-up is no longer medically necessary.

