#### 11.2.4 Reporting Serious Adverse Events

SAEs will be reported promptly, using the SAE Report Form, once the Investigator determines that the event meets the protocol definition of an SAE. The Investigator or designee will report the SAE **within 24 hours of his/her becoming aware of these events regardless of relationship of the SAE to the use of study drug**, in accordance with the instructions in the Study Reference Manual. The Investigator will always provide an assessment of relatedness at the time of the initial report as described in Section 11.2.2. The SAE Report will always be completed as thoroughly as possible with all available details of the event within the designated time frames. Copies of relevant patient records, autopsy reports, and other documents may be requested.

If the Investigator does not have all information regarding an SAE, he/she will not wait to receive additional information before reporting the SAE. The SAE Report will be updated when additional information is received **within 24 hours of receipt of such information**.

**Important:** For fatal and life-threatening events, the Sponsor's Medical Responsible Person should be contacted immediately. A death occurring during the study or information related to such occurrence that comes to the attention of the Investigator during the study must be reported immediately to the Sponsor. Contact numbers will be provided to the site, with a detailed SAE reporting procedure to be included in the Study Reference Manual (SRM), before any patients are consented.

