	A 50% increase in palpable distance, below LCM, for baseline splenomegaly of >10 cm or
	Leukaemic transformation confirmed by a bone marrow blast count of ≥20% or
	A peripheral blood blast content of ≥20% associated with an absolute blast count of ≥1 x 10  /L that lasts for at least 2 weeks
Stable disease	Belonging to none of the above listed response categories
Relapse	No longer meeting criteria for at least CI after achieving CR, PR, or CI, or
	Loss of anaemia response persisting for at least 1 month or
	Loss of spleen response persisting for at least 1 month

EMH, extramedullary haematopoiesis (no evidence of EMH implies the absence of pathology- or imaging study-proven non-hepatosplenic EMH); LCM, left costal margin; UNL, upper normal limit.

\*Baseline and post-treatment bone marrow slides are to be interpreted at one sitting by a central review process.

†Grading of MF is according to the European classification Thiele *et al.* European consensus on grading bone marrow fibrosis and assessment of cellularity. It is underscored that the consensus definition of a CR bone marrow is to be used only in those patients in which all other criteria are met, including resolution of leukoerythroblastosis.

‡Immature myeloid cells constitute blasts + promyelocytes + myelocytes + metamyelocytes + nucleated red blood cells. In splenectomized patients, <5% immature myeloid cells are allowed.

§See above for definitions of anaemia response, spleen response, and progressive disease. Increase in severity of anaemia constitutes the occurrence of new transfusion dependency or a ≥20 g/L decrease in haemoglobin level from pretreatment baseline that lasts for at least 12 weeks. Increase in severity of thrombocytopenia or neutropenia is defined as a 2-grade decline, from pretreatment baseline, in platelet or absolute neutrophil count, according to the Common Terminology Criteria for Adverse Events (CTCAE) version 4.0. In addition, assignment to CI requires a minimum platelet count of ≥25000 x 10^9/L and absolute neutrophil count of ≥0.5 x 10^9/L.

¶Applicable only to patients with baseline haemoglobin of <100 g/L.

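### Protocol 11.2 and 11.2.3 use three different tests to exclude disease progression, so leukaemic transformation, and admissions or deaths attributed to disease, can be left out of the AE and SAE data

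*Protocol*

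**What the plan says.** Four parts of the protocol bear on this.

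- **AE rule, Protocol 11.2.** "Progression of underlying malignancy is not reported as an AE if it is consistent with the suspected progression of the underlying cancer". A safeguard follows: "If there is any uncertainty about an AE being due to only the disease under study, it should be reported as an AE".
- **SAE rule, closing note of Protocol 11.2.3.** For admissions: "Hospitalization consistent with progression of underlying malignancy should NOT be reported as an SAE". For deaths: "An SAE with an outcome of death solely due to progression of the underlying malignancy does not need to be reported as an SAE".
- **Response criteria, Protocol 16.7.** The progressive disease list includes this item: "Leukaemic transformation confirmed by a bone marrow blast count of" 20% or more. Section 11 neither names transformation nor refers to 16.7 for what counts as progression when AEs are reported.
- **Notification of deaths, Protocol 11.2.4.** Any death that comes to the investigator's attention "during the study must be reported immediately to the Sponsor".

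Protocol 12.4.1 and SAP IX assess safety and tolerability, a primary objective, through AEs together with changes in physical examination, vital signs and laboratory values. SAP IX.B builds its tables from the AEs reported on the eCRF.

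**The concern.** The exclusions act before relatedness is assessed. Protocol 11.2.2 requires an AE to be recorded even when the investigator sees no link to the drug, and its unrelated category covers expected outcomes of existing disease. The progression rules in 11.2 and 11.2.3 bypass that step: an event put down to progression may never reach the AE form.

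Attribution is hard in this trial, on the protocol's own account. Section 3.1 says of myelofibrosis: "Death most often results from the consequences of thrombocytopenia or neutropenia, haemorrhage or infection". Section 5.1.1 titrates the drug to a reduced platelet count. Section 8.2.1 expects lower neutrophil counts and treats such haematologic effects as pharmacodynamic rather than adverse. Section 3.5 accepts that blood and marrow findings on this drug may be misread. The study is open-label with no control arm, and the visible text describes no independent adjudication of cause.

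Transformation is also foreseeable. Section 3.1 names evolution to AML as a major complication, and Section 6.1.1 admits patients with up to 10% peripheral blasts. At stake is whether the AE and SAE tables give a full count of the most serious outcomes.

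**Working it through.** **Step 1. The tests side by side**

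| Event | Section | When it is excluded | Force of the rule |
|---|---|---|---|
| Progression as an AE | 11.2 | Fits suspected progression, unless there is any doubt that disease is the only cause | Not reported; doubt means report |
| Death as an SAE | 11.2.3 note | Progression is the sole cause | Permissive: need not be reported |
| Hospitalisation as an SAE | 11.2.3 note | Merely fits progression; no exception for doubt | Prohibitive: should not be reported |

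**Step 2. Apply them to two cases**

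*Admission with infection during neutropenia.* Suppose the investigator thinks it fits advancing disease but cannot rule out the drug. Under 11.2 it is an AE. If the patient dies, progression is not the sole cause and the SAE exception does not apply. If the patient recovers, the hospitalisation sentence says it is not an SAE, unless another seriousness criterion is met. The same uncertainty leads to opposite answers.

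*Marrow-confirmed transformation.* Under 16.7 this is progressive disease. An investigator with no doubt about cause may leave it off the AE form and comply with 11.2; one with doubt must report it. The recorded count then depends on individual judgement.

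**Step 3. Scale (illustration only)**

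The plan states no event rate or attribution share, so there is no figure of its own to reproduce. The sample size is about 75 treated patients (Protocol 6.2, SAP IV.C).

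- One event is 1/75 = 1.3 percentage points.
- With 0 events recorded, the exact (Clopper-Pearson) upper 95% limit is 1 − 0.025^(1/75) = 4.8%.
- If 3 events had been omitted, the true figure is 3/75 = 4.0% (exact 95% CI 0.8% to 11.2%). If 5, it is 5/75 = 6.7% (2.2% to 14.9%).

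For an assumed true rate p and an assumed share f attributed to progression and omitted, the chance that none of 75 patients shows a recorded event is (1 − p(1 − f))^75:

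| p | f = 0 | f = 50% | f = 75% | f = 100% |
|---|---|---|---|---|
| 2% | 22% | 47% | 69% | 100% |
| 5% | 2% | 15% | 39% | 100% |
| 10% | <0.1% | 2% | 15% | 100% |

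**Step 4. Are deaths plausible in the window?**

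Take 169 days of treatment plus 28 of follow-up = 197 days, and treat the 5.5-year median survival in Protocol 3.1 as a constant hazard. Then 1 − exp(−ln 2 × 197 / (365.25 × 5.5)) = 6.6%, or 4.9 of 75. That median runs from diagnosis, so it may not fit a pretreated population. Assumed medians of 2.5 and 1.5 years give 10.4 and 16.6 deaths. The 197-day window is the Phase 2b one without the additional treatment period; Phase 1/2a treatment was 85 days.

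**The case against.** The strongest defence is that the safeguard in 11.2 concerns cause, not diagnosis. A confirmed blast count does not show that disease alone was responsible, so a doubtful transformation belongs in the AE data. A death from bleeding or infection that could be due to the drug is likewise not solely due to progression. This stands: the hardest cases are directed to AE reporting. It does not help when an investigator is confident of a disease cause, and the hospitalisation sentence carries no such safeguard.

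Section 16.7 also lists only spleen and blast criteria, so bleeding and infection are not progression by that list. That is fair, but Section 11 does not adopt the list, so sites have no stated definition to apply.

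The outcomes are also partly captured elsewhere: blood counts with differential, scheduled marrow samples, discontinuation for treatment failure, at least quarterly DSMC/SAB review, and survival estimates if applicable (Protocol 12.7). These reduce the risk of loss to the trial but do not put the events in the AE and SAE tables.

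Four stronger readings are tempting and are not supported:

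- *Transformation is excluded by rule.* This is an inference from 11.2 and 16.7 together; Section 11 never says so.
- *Sections 11.2.3 and 11.2.4 contradict each other on deaths.* Notifying the sponsor and classifying an event as an SAE are different acts, and both rules can be followed.
- *The primary safety result is biased downwards.* The documents show only that it could be. The three-event example is assumed.
- *The SAP has no table of deaths or transformations.* Parts of its disposition, efficacy and AE sections are redacted, so absence cannot be asserted.

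**Conclusion.** The concern holds as a defect in the reporting rules. The three tests do not agree. The hospitalisation test is the loosest and is worded as a prohibition, so it undercuts both the uncertainty safeguard in 11.2 and the sole-cause limit for deaths. Because transformation counts as progressive disease and Section 11 does not exempt it, a site can leave it, and admissions or deaths it attributes to disease, out of the AE and SAE data without breaching the protocol.

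The size is unknown. Any figure depends on an event rate and an attribution share that the documents do not give. The contrast of 4.0% with a tabulated 0% only shows that, with 75 patients, a few omitted events would change how the safety table reads.

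**What to change.** 1. **Protocol 11.2 and 11.2.3:** reconcile the passages so that the hospitalisation exception uses the death test (progression as the sole cause), with any uncertainty reported.
2. **Protocol 11.2:** state that leukaemic transformation and every death from first dose to the End of Study visit are recorded on the eCRF, with attributed cause as a separate field.
3. **SAP IX.B:** unless the redacted text already does so, tabulate all-cause deaths and leukaemic transformations for the Safety population with exact confidence intervals, showing attributed cause.

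The cost is a few more forms and one table. Reported SAE rates will be somewhat higher, and the report should say that this follows from fuller capture.

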#### 11.2.4 Reporting Serious Adverse Events

SAEs will be reported promptly, using the SAE Report Form, once the Investigator determines that the event meets the protocol definition of an SAE. The Investigator or designee will report the SAE **within 24 hours of his/her becoming aware of these events regardless of relationship of the SAE to the use of study drug**, in accordance with the instructions in the Study Reference Manual. The Investigator will always provide an assessment of relatedness at the time of the initial report as described in Section 11.2.2. The SAE Report will always be completed as thoroughly as possible with all available details of the event within the designated time frames. Copies of relevant patient records, autopsy reports, and other documents may be requested.

If the Investigator does not have all information regarding an SAE, he/she will not wait to receive additional information before reporting the SAE. The SAE Report will be updated when additional information is received **within 24 hours of receipt of such information**.

**Important:** For fatal and life-threatening events, the Sponsor's Medical Responsible Person should be contacted immediately. A death occurring during the study or information related to such occurrence that comes to the attention of the Investigator during the study must be reported immediately to the Sponsor. Contact numbers will be provided to the site, with a detailed SAE reporting procedure to be included in the Study Reference Manual (SRM), before any patients are consented.

#### Table 5: Serious Adverse Event Reporting Contact Details

PPD

Additionally, the Institutional Review Board (IRB), Independent Ethics Committee (IEC) and Human Research Ethics Committee (HREC), as applicable, must be notified in writing of any SAEs that require expedited reporting to Regulatory Authorities. Depending upon regional requirements, it is the responsibility of either the Investigator or Imago BioSciences to notify the IRB/IEC/HREC. All SAEs meeting expedited reporting requirements will be reported to appropriate regulatory agencies by Imago BioSciences or their designee as soon as possible and within the timeframes specified in the various regions in which the study is to be conducted.

## 12 ANALYSIS AND STATISTICAL CONSIDERATIONS

### 12.1 General Considerations

Detailed methodology for summary and statistical analyses of the data collected in this trial will be documented in a Statistical Analysis Plan (SAP). Additionally, a Pharmacokinetic Analysis Plan (PKAP) will be prepared. These documents may modify the plans outlined in the protocol; however, any major modifications of the primary endpoints definition and/or its analysis will also be reflected in a protocol amendment. Additional statistical analyses other than those described in this section may be performed if deemed appropriate and included in the SAP/PKAP.

### 12.2 Power

This study is designed to make an assessment of the safety, tolerability, and pharmacokinetics of the capsule formulation of IMG-7289. The number of patients is sufficiently powered to determine mean pharmacokinetic parameters. Given that all pharmacodynamic (PD) metrics are exploratory in nature, the study is not powered to make statements about the statistical significance of any changes observed.

### 12.3 Treatment Assignment and Blinding

This is an open-label study. The Investigators, other hospital personnel, patients and Sponsor will know the identity of the treatment.

Effort will be made, as appropriate, to maintain continuity of study staff who administer/evaluate various assessments at each site (i.e., physical examination, morphology/fibrosis grade review, etc.), in order to facilitate consistency of assessments within a patient.

### 12.4 Study Endpoints

#### 12.4.1 Primary Endpoints

- The safety and tolerability of IMG-7289 will be assessed by the analysis of adverse events (AEs), as well as changes in physical examinations, vital signs and laboratory values CCI 

CCI 

CCI

**Note:** In the UK, serious AEs (SAEs) will be recorded from time of consent through the EoS or until the Investigator and Imago BioSciences determine that follow-up is no longer necessary.

- Changes in physical examinations, vital signs and laboratory values will also be evaluated and assessed from Screening/Baseline until EoS/ET. Information on the timing of these assessments is presented in the schedule of assessment. CCI
- 

CCI

- Pharmacokinetic (PK) parameters will be determined in accordance with earlier protocol versions and the PKAP associated with the study (Phase 1/2a only).
- Reduction in spleen volume will be assessed based on spleen volume measured by MRI (or CT scan where applicable) from Day 0, and spleen size measured by palpation from Baseline, to each visit where the variables are measured.

**Note:** In Germany, use of computerised tomography (CT) is not permitted for patients unable to undergo magnetic resonance imaging (MRI). Only MRI is permitted for study purposes.

CCI

CCI

### **12.5 Safety and Tolerability Data**

Demographics will be tabulated and summarized. Medical and surgical history data at Screening will be listed, as will Physical Examination data (including height and weight) at Screening, and at subsequent visits. All characteristics at baseline such as age, weight, height and vital signs (resting heart rate, semi-supine systolic/diastolic blood pressure, respiratory rate and temperature) parameters will be tabulated and summarized.

All patients receiving at least one dose of IMG-7289 will be included in the safety analysis.

Laboratory values outside the laboratory normal ranges will be summarized and assessed for change from Day 0 and trends indicating a safety signal.

Treatment-emergent adverse events will be coded using the Medical Dictionary for Regulatory Activities (MedDRA) and summarized for the number of patients reporting the AE and the number of AEs reported. A by-patient AE data listing including (but not limited to) verbatim term, coded term, severity, and relationship to treatment will be provided.

Concomitant medications will be listed by patient and coded using the WHO drug dictionary. Medical history will be listed by patient.

Descriptive statistics (arithmetic mean, standard deviation (SD), sample size, CV (coefficient of variation), median, minimum, maximum, and number) will be calculated for quantitative safety data as well as for the differences to baseline, when appropriate. In addition, a shift table describing out of normal range shifts will be provided for clinical laboratory results and physical examination results. For safety and tolerability, missing data including those not obtained because of death will be the last value carried forward.

